12. STATISTICAL METHODS

Statistical analysis will be done by the sponsor or under the authority of the sponsor. A general description of the statistical methods to be used to analyze the efficacy and safety data is outlined below. Specific details will be provided in the Statistical Analysis Plan.

Summary statistics for continuous variables will include the mean, standard deviation, median, and range. Categorical data will be presented as frequencies and percentages.

12.1. Subject Information

The analysis populations for this study are defined as:

- The Treated Population will consist of all subjects who receive at least 1 dose of study drug (either ibrutinib or nivolumab). The Treated Population will be used for all safety and efficacy analysis unless otherwise stated.
- The Response Evaluable Population will consist of all subjects who receive at least 1 dose of both study drugs (ibrutinib and nivolumab), and have a pretreatment, and at least 1 posttreatment disease assessment; unless no post-baseline scan was performed due to AE possibly related to treatment.
- The Pharmacokinetic/Pharmacodynamic Population will consist of all subjects who receive at least 1 dose of study drug (either ibrutinib or nivolumab) and have at least 1 posttreatment sample collected during treatment to determine the concentration or pharmacodynamic biomarker response.

12.2. Safety Analyses

Adverse Events

The verbatim terms used in the eCRF by investigators to identify AEs will be coded using the most current version of the Medical Dictionary for Regulatory Activities (MedDRA). Toxicities will be graded for severity according to NCI-CTCAE, version 4. All reported AEs with onset during the Treatment Period (ie, treatment-emergent adverse events [TEAEs], and AEs that have worsened since baseline) will be included in the analysis.

Specifically, the following will be summarized:

- Incidence of DLT (Part A)
- All adverse events
- Grade 3 or higher adverse events
- Serious adverse events
- Adverse events leading to discontinuation of treatment

- Adverse events leading to death
- Adverse events of special interest

Summaries, listings, datasets, or subject narratives may be provided, as appropriate, for those subjects who die, who discontinue treatment due to an adverse event, or who experience a severe or a SAE.

Clinical Laboratory Tests

Laboratory data will be summarized by type of laboratory test. Reference ranges and markedly abnormal results (specified in the Statistical Analysis Plan) will be used in the summary of laboratory data. Descriptive statistics will be calculated for each laboratory analyte at baseline. Parameters with predefined toxicity grades will be summarized. Change from baseline to the worst grade experienced by the subject during the study will be provided as shift tables.

Vital Signs

Descriptive statistics of heart rate and blood pressure (systolic and diastolic) (supine) values and changes from baseline will be summarized. The percentage of subjects with clinically important changes from baseline will be summarized.

12.3. Sample Size Determination

This is a Phase 1/2a dose optimization and expansion study. For Part A, a statistical design based on the approach described in Ji, et al. (2010)³⁰ and Ji and Wang (2013)^{29,30} will be used. This method requires a definition of an equivalence interval (EI), $[0.25; 0.30]$, in which any dose is considered as a potential candidate for the true MTD, where 0.30 is the targeted DLT rate. Defining an EI results in the partition of the unit interval $(0, 1)$ into 3 subintervals; $(0; 0.25)$, $[0.25, 0.30]$, and $(0.30; 1)$. Doses in these 3 intervals are deemed lower, close to, and higher than the MTD, respectively. At least 6, and up to 9 subjects may be treated in each cohort in Part A. Approximately 18 subjects may be enrolled in Part A.

Part B, Cohorts B1 (CLL/SLL), B2 (FL), B3 (DLBCL), and B4 (Richter syndrome) are designed to evaluate the feasibility and safety of treating subjects with ibrutinib in combination with nivolumab and to evaluate preliminary activity. The sample size is calculated based on the following assumptions (denoting the true response rate of ibrutinib in combination with nivolumab as p):

- The overall response rate under null hypothesis is 20%
- The overall response rate under alternative hypothesis is at least 38%
- The probability to mistakenly rejecting the null hypothesis when it is actually true is 0.1 (one-sided).
- The probability to correctly rejecting null hypothesis when alternative hypothesis is true is at least 0.8

Under the above assumptions, the study will enroll approximately 35 subjects to get at least 32 response-evaluable subjects in each cohort of Part B (dose expansion; Cohorts B1, B2, B3, and B4).

Approximately 158 subjects (with up to 18 subjects in Part A and approximately 140 subjects in the Part B, dose expansion) will be enrolled in this study.

12.4. Efficacy Analyses

Part A: Individual best tumor responses and duration of response (defined as the time from first response to progression) will be listed for each dose cohort.

Part B: The following efficacy analyses will be performed to explore the clinical activity of ibrutinib in combination with nivolumab in each cohort in the treated population unless otherwise stated:

- Overall response rate (CR or PR) will be calculated with 95% CI for each disease-specific cohort B1, B2, B3, and B4 on the response-evaluable population.
- Progression-free survival and overall survival at 1 year will be evaluated using Kaplan-Meier method.
- Duration of response and duration of stable disease will be evaluated if there are sufficient data for responders within each cohort.

12.5. Pharmacokinetic Analyses

The plasma concentration data for ibrutinib and, if possible and judged relevant, the metabolite PCI-45227, and serum concentrations of nivolumab at each timepoint will be summarized using descriptive statistics. Ibrutinib and nivolumab data will be listed by dose cohort for all subjects with available plasma/serum concentrations. Subjects will be excluded from the pharmacokinetic analysis if their data do not allow for accurate assessment of the pharmacokinetic (eg, incomplete administration of the study agent; concentration data not sufficient for pharmacokinetic parameter calculation due to missing pharmacokinetic draws at multiple visits; or early discontinuation from the study).

All concentrations below the lowest quantifiable concentration or missing data will be labeled as such in the concentration data presentation. Concentrations below the lowest quantifiable concentration will be treated as zero in the summary statistics and for the calculation of pharmacokinetic parameters. All subjects and samples excluded from the analysis will be clearly documented in the study report.

If non-compartmental analysis for ibrutinib/PCI-45227 is performed, results will be summarized using descriptive statistics.

Population pharmacokinetic analysis of ibrutinib plasma concentration-time data may be performed using NONMEM. Data may be combined with data from other studies to support a relevant structural population-based pharmacokinetic model. Available subject characteristics

(demographics, laboratory variables, genotypes, etc.) will be tested as potential covariates affecting pharmacokinetic parameters.

Model-derived exposure parameters may be subjected to further explore pharmacokinetic/pharmacodynamic correlation between exposure with relevant clinical or biomarker information.

Ibrutinib and nivolumab concentration data may be compared to observed concentration data and/or concentration estimates from the existing population PK models of ibrutinib/nivolumab, as appropriate.

If additional population PK analyses of ibrutinib and/or nivolumab are performed using data from this study, the results relevant for this study will be communicated, but an additional modeling report may be generated and will not be part of the study report for this study.

12.6. Biomarker Analyses

Analyses are planned to identify biomarkers that are indicative of the mechanisms of action of the drug or predictive of efficacy for the combination. The associations of biomarkers with clinical response or time-to-event endpoints will be assessed using the appropriate statistical methods (analysis of variance [ANOVA], categorical, or survival model), depending on the endpoint. Correlation of baseline expression levels or changes in expression levels with response or time-to-event endpoints will identify responsive (or resistant) subgroups.

12.7. Study Evaluation Team

The SET will monitor data on an ongoing basis during dose optimization to ensure the continuing safety of the subjects enrolled in the study. The SET will consist of the principal investigators, sponsor medical monitors, the sponsor's clinical pharmacologist, or their designees, and the sponsor's statistician. Medical safety assessment representatives or other functions experts will be consulted as needed.

The SET will convene regularly; and at a minimum after each dose level completes the DLT assessment period. The SET may convene at additional times for data review or for any safety-related issues; a SET meeting can be requested by any SET member. In addition the SET and additional functional representatives from Janssen, as applicable, may review the data for expansion cohorts (Part B) for the efficacy endpoints including but not limited to ORR along with any safety concerns.

See Section 3.3 for further details on the SET decision-making process.

13. ADVERSE EVENT REPORTING

Timely, accurate, and complete reporting and analysis of safety information from clinical studies are crucial for the protection of subjects, investigators, and the sponsor, and are mandated by regulatory agencies worldwide. The sponsor has established Standard Operating Procedures in conformity with regulatory requirements worldwide to ensure appropriate reporting of safety

information; all clinical studies conducted by the sponsor or its affiliates will be conducted in accordance with those procedures.

Method of Detecting Adverse Events and Serious Adverse Events

Care will be taken not to introduce bias when detecting adverse events or serious adverse events. Open-ended and nonleading verbal questioning of the subject is the preferred method to inquire about adverse event occurrence.

Solicited Adverse Events

Solicited adverse events are predefined local and systemic events for which the subject is specifically questioned.

Unsolicited Adverse Events

Unsolicited adverse events are all adverse events for which the subject is specifically not questioned.

13.1. Definitions

13.1.1. Adverse Event Definitions and Classifications

Adverse Event

An adverse event is any untoward medical occurrence in a clinical study subject administered a medicinal (investigational or non-investigational) product. An adverse event does not necessarily have a causal relationship with the treatment. An adverse event can therefore be any unfavorable and unintended sign (including an abnormal finding), symptom, or disease temporally associated with the use of a medicinal (investigational or non-investigational) product, whether or not related to that medicinal (investigational or non-investigational) product. (Definition per International Conference on Harmonisation [ICH])

This includes any occurrence that is new in onset or aggravated in severity or frequency from the baseline condition, or abnormal results of diagnostic procedures, including laboratory test abnormalities.

Note: The sponsor collects adverse events starting with the signing of the ICF (refer to Section 13.3.1, All Adverse Events, for time of last adverse event recording).

Serious Adverse Event

A serious adverse event based on ICH and EU Guidelines on Pharmacovigilance for Medicinal Products for Human Use is any untoward medical occurrence that at any dose:

- Results in death
- Is life-threatening
(The subject was at risk of death at the time of the event. It does not refer to an event that hypothetically might have caused death if it were more severe.)
- Requires inpatient hospitalization or prolongation of existing hospitalization
- Results in persistent or significant disability/incapacity
- Is a congenital anomaly/birth defect
- Development of a new malignancy that is not associated with the disease under study
- Is a suspected transmission of any infectious agent via a medicinal product
- Is Medically Important*

*Medical and scientific judgment should be exercised in deciding whether expedited reporting is also appropriate in other situations, such as important medical events that may not be immediately life threatening or result in death or hospitalization but may jeopardize the subject or may require intervention to prevent one of the other outcomes listed in the definition above. These should usually be considered serious.

If a serious and unexpected adverse event occurs for which there is evidence suggesting a causal relationship between the study drug and the event (eg, death from anaphylaxis), the event must be reported as a serious and unexpected suspected adverse reaction even if it is a component of the study endpoint (eg, all-cause mortality).

Unlisted (Unexpected) Adverse Event/Reference Safety Information

An adverse event is considered unlisted if the nature or severity is not consistent with the applicable product reference safety information. For ibrutinib and nivolumab, the expectedness of an adverse event will be determined by whether or not it is listed in the respective Investigator's Brochure.

Adverse Event Associated With the Use of the Drug

An adverse event is considered associated with the use of the drug if the attribution is possible, probable, or very likely by the definitions listed in Section 13.1.2.

13.1.2. Attribution Definitions

Not Related

An adverse event that is not related to the use of the drug.

Doubtful

An adverse event for which an alternative explanation is more likely, eg, concomitant drug(s), concomitant disease(s), or the relationship in time suggests that a causal relationship is unlikely.

Possible

An adverse event that might be due to the use of the drug. An alternative explanation, eg, concomitant drug(s), concomitant disease(s), is inconclusive. The relationship in time is reasonable; therefore, the causal relationship cannot be excluded.

Probable

An adverse event that might be due to the use of the drug. The relationship in time is suggestive (eg, confirmed by dechallenge). An alternative explanation is less likely, eg, concomitant drug(s), concomitant disease(s).

Very Likely

An adverse event that is listed as a possible adverse reaction and cannot be reasonably explained by an alternative explanation, eg, concomitant drug(s), concomitant disease(s). The relationship in time is very suggestive (eg, it is confirmed by dechallenge and rechallenge).

13.1.3. Severity Criteria

The severity assessment for an adverse event or serious adverse event should be completed using the NCI CTCAE Version 4. Any adverse event or serious adverse event not listed in the NCI CTCAE Version 4 will be graded according to investigator clinical judgment by using the standard grades as follows:

Grade 1 (Mild): Awareness of symptoms that are easily tolerated, causing minimal discomfort and not interfering with everyday activities.

Grade 2 (Moderate): Sufficient discomfort is present to cause interference with normal activity.

Grade 3 (Severe): Extreme distress, causing significant impairment of functioning or incapacitation. Prevents normal everyday activities.

Grade 4: Life-threatening or disabling adverse event

Grade 5: Death related to the adverse event

The investigator should use clinical judgment in assessing the severity of events not directly experienced by the subject (eg, laboratory abnormalities).

13.2. Special Reporting Situations

Special reporting situations should be recorded in the eCRF. Any special reporting situation that meets the criteria of a serious adverse event should be recorded on the serious adverse event page of the eCRF.

13.2.1. Nivolumab

For instructions on how to handle events of clinical interest related to nivolumab, please refer to Section 8 and the nivolumab Investigator's Brochure, Appendix 2. These events (Grade ≥ 3) will be reported using the same timelines used for reporting SAEs. These events include:

- Colitis
- Endocrine
- Uveitis
- Hepatic
- Pneumonitis
- Renal
- Skin
- Immune-related AEs

13.2.2. Other

Other safety events of interest on a sponsor study drug that may require expedited reporting and/or safety evaluation include, but are not limited to:

- Overdose of a sponsor study drug
- Suspected abuse/misuse of a sponsor study drug
- Accidental or occupational exposure to a sponsor study drug
- Medication error involving a sponsor product (with or without subject/patient exposure to the sponsor study drug, eg, name confusion)

13.3. Procedures

13.3.1. All Adverse Events

All adverse events and special reporting situations, whether serious or non-serious, will be reported from the time a signed and dated ICF is obtained until 30 days after the last dose of ibrutinib or 100 days after the last nivolumab infusion, whichever is later. Afterwards, report only SAEs that are at least possibly related to study treatment. After the clinical cutoff, only SAEs and Grade ≥ 3 AEs will be collected. Serious adverse events, including those spontaneously reported to the investigator within 30 days after the last dose of study therapy, must be reported using the Serious Adverse Event Form. The sponsor will evaluate any safety information that is spontaneously reported by an investigator beyond the time frame specified in the protocol.

Disease progression should not be recorded as an adverse event or serious adverse event term; instead, signs and symptoms of clinical sequelae resulting from disease progression/lack of efficacy will be reported if they fulfill the serious adverse event definition (refer to Section 13.1.1). Death should not be recorded as an adverse event or serious adverse event, but as the outcome of an adverse event. The event that resulted in the death should be reported as a serious adverse event.

All events that meet the definition of a serious adverse event will be reported as serious adverse events, regardless of whether they are protocol-specific assessments.

All adverse events, regardless of seriousness, severity, or presumed relationship to study drug, must be recorded using medical terminology in the source document and eCRF; reporting on eCRF after CCO (per amendment #6 and 7 further revisions apply per [Table 1](#)[collection of SAEs and Grade ≥ 3 AEs, AEs leading to discontinuation or modification, laboratory assessments {Grade ≥ 3 or clinically significant}]). Whenever possible, diagnoses should be given when signs and symptoms are due to a common etiology (eg, cough, runny nose, sneezing, sore throat, and head congestion should be reported as "upper respiratory infection"). Investigators must record in the eCRF their opinion concerning the relationship of the adverse event to study therapy. All measures required for adverse event management must be recorded in the source document and reported according to sponsor instructions.

The sponsor assumes responsibility for appropriate reporting of adverse events to the regulatory authorities. The sponsor will also report to the investigator (and the head of the investigational institute where required) all suspected unexpected serious adverse events that are unlisted (unexpected) and associated with the use of the study drug. The investigator (or sponsor where required) must report these events to the appropriate Independent Ethics Committee/Institutional Review Board (IEC/IRB) that approved the protocol unless otherwise required and documented by the IEC/IRB.

For all studies with an outpatient phase, the subject must be provided with a "wallet (study) card" and instructed to carry this card with them for the duration of the study indicating the following:

- Study number
- Statement, in the local language(s), that the subject is participating in a clinical study
- Investigator's name and 24-hour contact telephone number
- Local sponsor's name and 24-hour contact telephone number (for medical staff only)
- Site number
- Subject number

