- Overall response rate (CR or PR) will be calculated with 95% CI for each disease-specific cohort (B1, B2, B3, and B4) on the response-evaluable population.
- Progression-free survival and overall survival at 1 year will be evaluated using Kaplan-Meier method.
- Duration of response and duration of stable disease will be evaluated if there are sufficient data for responders within each cohort.

Table 1: Time and Events Schedule

| | Notes | Screening Period | Treatment Period (14 day cycles) | | | Follow-up Period ^a |
|---|--|---|---|--------------------------|-----|-------------------------------|
| | | up to 28 days before start of any study treatment | BASELINE ASSESSMENT CID1 (without run-in phase) CID-7 (with run-in phase) | Day 1, subsequent cycles | EOT | Q3m |
| 
Treatment Period begins with the first administration of study therapy. EOT visit is required for all subjects and should take place within 30 days after last dose of study therapy with a window of ± 7 days. If the subject requires subsequent anti-lymphoma/neoplastic therapy in the interim period between last dose of study drug and the EOT visit, then this visit should be completed just prior to initiation of subsequent therapy. Follow-up visits in all subjects will be completed every 3 months with a window of ± 7 days until death or end of study. Note that the first FU visit should be approximately 100 days after end of nivolumab therapy; during this first FU visit, additional sampling will be done.
 
After the clinical cutoff, subjects who are ongoing on treatment continue all assessment per protocol, however data collected on eCRF will be limited to at least: SAEs and AEs Grade ≥ 3, laboratory assessments (Grade ≥ 3 or clinically significant), efficacy assessments, survival status, and study treatment administration.
 
Per Amendment 7, subjects who are receiving study treatment will continue all assessments per protocol. Data collected in the eCRF will be further limited to: SAEs and Grade ≥ 3 AEs that are at least possibly related to treatment, AEs leading to discontinuation or modification, efficacy assessments, and study treatment administration.
 | | | | | | |
| Screening/Administrative | | | | | | |
| Informed consent | ICF must be signed before any study-related procedures are performed. | X | | | | |
| Eligibility criteria | | X | | | | |
| Demography/ Medical History | | X | | | | |
| Study Drug Administration | | | | | | |

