The primary analysis of the study will be performed 6 months after the last subject has received the first dose of study medication, or earlier if that subject discontinues study therapy. After the cutoff for primary analysis, subjects who are receiving study treatment can continue treatment per protocol until progression, unacceptable toxicity, withdrawal of consent, or other reason as listed in Section 11.2. End of study is defined as the last subject who completed the EOT Treatment assessment.

After the clinical cutoff at a minimum the following data will be collected on eCRF: SAEs and AEs Grade ≥ 3 , laboratory assessments (Grade ≥ 3 or clinically significant), efficacy, survival status, and treatment administration. Data collected from the primary analysis until end of study will be summarized in a clinical study report addendum.

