13.3.3. Adverse Events of Special Interest (AESI)

Specific adverse events or groups of adverse events will be followed as part of standard safety monitoring activities by the Sponsor. These events will be reported to the sponsor within 24 hours of awareness irrespective of seriousness (ie, serious and nonserious adverse events) following the procedure described above for serious adverse events and will require enhanced data collection.

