13.3.3.1. Major Hemorrhage

Major hemorrhage is defined as: Treatment-emergent hemorrhagic adverse events of Grade 3 or higher.

- Any treatment-emergent hemorrhagic adverse events of Grade 3 or higher. All hemorrhagic events requiring a transfusion of red blood cells should be reported as Grade 3 or higher AE per CTCAE.
- Any treatment-emergent serious adverse event of bleeding of any grade.
- Any treatment-emergent central nervous system hemorrhage/hematoma of any grade.

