5.2. Adverse Events of Special

Adverse events of special interest to be summarized include the following:

Major Hemorrhage

Hemorrhage SMQ without labs will be used to identify bleeding events. Any grade ≥ 3 hemorrhage events, any SAE or all grades of CNS hemorrhage (preferred terms are listed in Appendix A). Events will be summarized by preferred terms.

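### Section 13.3.1 and Table 1 disagree on which AEs are collected after the clinical cutoff, and no list names AESIs, so AE counts in the addendum depend on the text a site follows

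*Protocol*

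**What the plan says.** The current protocol describes AE collection after the clinical cutoff in several places.

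- **Section 13.3.1, first paragraph:** "After the clinical cutoff, only SAEs and Grade ≥ 3 AEs will be collected". There is no causality condition and no exemption.
- **Section 13.3.1, bracket in a later paragraph:** for eCRF reporting after the cutoff it points to Table 1 for Amendments 6 and 7. It lists SAEs, Grade ≥3 AEs, AEs that led to stopping or changing treatment, and laboratory results that are Grade ≥3 or of clinical significance.
- **Table 1 header, first note (after the cutoff):** "data collected on eCRF will be limited to at least" SAEs, Grade ≥3 AEs, the same laboratory results, efficacy, survival status and study treatment. Section 3.1 has a similar list, introduced by "After the clinical cutoff at a minimum the following data will be collected on eCRF".
- **Table 1 header, Amendment 7 note:** a further restriction to SAEs and Grade ≥3 AEs "that are at least possibly related to treatment, AEs leading to discontinuation or modification", efficacy and study treatment. Laboratory results and survival status are no longer listed.

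On AESIs, Section 13.3.3 says: "These events will be reported to the sponsor within 24 hours of awareness irrespective of seriousness (ie, serious and nonserious adverse events"). It uses the SAE procedure, asks for enhanced data collection, and sets no cutoff date. Section 13.3.3.1 includes in major haemorrhage "Any treatment-emergent central nervous system hemorrhage/hematoma of any grade". SAP 5.2 likewise summarises "any SAE or all grades of CNS hemorrhage". Section 3.1 and SAP 4.1.3 send post-cutoff data to an addendum to the clinical study report.

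**The concern.** An AE rate can be interpreted only if the rule that admits an event is known and was the same at every site. Here one site could follow the 13.3.1 sentence, another its bracket, and a third Table 1. The addendum would then mix all-cause counts with counts filtered by the causality opinion of an investigator in an open-label study, and no label would show which is which.

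The AESI problem is related but narrower. Major haemorrhage is the one AESI defined in Section 13.3.3.1, and Section 1.2.2 mentions intracranial haemorrhage with ibrutinib. One part of its definition is independent of grade and seriousness, whereas the post-cutoff lists select on grade, seriousness or effect on treatment. The SAP summary can therefore call for events that the eCRF lists do not request.

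**Working it through.** The plan states no figure to reproduce. The check is to take typical post-cutoff events and ask what each text does with them.

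| Event after the cutoff | 13.3.1 sentence | 13.3.1 bracket | Table 1, first note | Table 1, Amendment 7 note |
|---|---|---|---|---|
| Non-serious Grade 3 AE, unrelated, no change to treatment | collected | collected | collected | not collected |
| Non-serious Grade 2 AE that led to a dose hold | not collected | collected | not named (list is a minimum) | collected |
| Unrelated SAE, no change to treatment | collected | collected | collected | depends on whether the causality phrase also covers SAEs |
| Non-serious Grade 1-2 CNS haemorrhage, no change to treatment | not collected | not named | not named (list is a minimum) | not named |

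**Causality.** The 13.3.1 sentence, its bracket and the first Table 1 note carry no causality condition, so they agree from the cutoff until Amendment 7. The conflict starts with the Amendment 7 note, which the bracket claims to reflect but whose condition it omits. The laboratory item in the bracket does have a source in Table 1, namely the first note. The bracket in effect merges two successive notes.

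**Events that changed treatment.** Here the conflict lies between the 13.3.1 sentence, whose wording excludes them, and both the bracket and the Amendment 7 note, which include them. Section 13.3.1 therefore disagrees with itself.

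**AESIs.** The fourth row is on no list. The stopped-or-changed category does not reliably catch it, because Table 8 lets study therapy continue for related Grade 1 haemorrhagic events and for Grade 2 events persisting up to 12 weeks. Section 13.3.3 does require the event to be sent to the sponsor, by the SAE procedure. Under Section 13.3.2 that means the Serious Adverse Event Form, with reports made by fax. SAP 5.1 codes AEs from verbatim terms in the CRF. No text says that a non-serious AESI reported on the form after the cutoff is also entered in the eCRF.

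**Size, by assumption only.** Let f be the fraction of post-Amendment 7 Grade ≥3 AEs judged at least possibly related. Then

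related-only count ≈ f × all-cause count,

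before adding back unrelated events that led to stopping or changing treatment and, on one reading, unrelated SAEs. With f = 0.3, 0.5 and 0.8 the Table 1 rule captures about 30%, 50% and 80% of what the 13.3.1 rule captures. The documents give no f, no post-cutoff AE count and no number of subjects still on treatment.

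**The case against.** The best defence is that the rules are mostly sequential and that precedence is given. Section 13.3.1 defers to Table 1, Table 1 ties the causality restriction to Amendment 7, and that restriction was deliberate: the amendment rationale cites an established safety profile and objectives already analysed and published. Much of this stands. It confines the causality conflict to the period after Amendment 7. It does not remove the conflict, because the deferral paraphrases Table 1 without the condition and sits in the same section as an unqualified sentence that says otherwise.

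Three stronger readings are tempting, and the documents do not support them.

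- **That low-grade CNS bleeds are lost after the cutoff.** Section 13.3.3 still requires them within 24 hours, "irrespective of seriousness (ie, serious and nonserious adverse events"), and Table 8 asks sites to contact the sponsor about related low-grade haemorrhagic events. Section 3.1 and the first Table 1 note also set a minimum. What is unsettled is entry in the eCRF.
- **That many subjects are affected, judging by the 15-month median CLL therapy the SAP expects.** Time on treatment at the cutoff says little about who was still treated when the causality restriction began.
- **That Grade ≥3 collection regardless of causality must be restored.** That would reverse a documented trade-off; it would not correct an error.

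It is also fair to say that the SAP does not state that the tables of SAP 5.1 and 5.2 will be rerun on pooled data for the addendum. Equally, it sets no rule against pooling. Analyses using data up to the clinical cutoff are not touched.

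**Conclusion.** The point stands as an inconsistency in current text, with a limited reach. After the cutoff, Section 13.3.1 contradicts its own bracket over AEs that changed treatment. After Amendment 7, Section 13.3.1 and Table 1 differ on causality. At no stage does a collection list name AESIs, so a non-serious Grade 1-2 CNS haemorrhage should reach the sponsor but may be missing from the eCRF data behind the SAP 5.2 summary.

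Only the addendum is exposed. The effect on Grade ≥3 rates could be large or small; the 30% to 80% range rests entirely on the assumed related fraction. Missed CNS bleeds are probably few, since some would qualify as medically important SAEs under Section 13.1.1. The matter should be corrected, but it does not threaten the primary results.

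**What to change.** 1. Replace the sentence and bracket in Section 13.3.1 and the notes in Table 1 with one identical list, split by period: cutoff to Amendment 7, and after Amendment 7. State whether the causality condition applies to SAEs as well as to Grade ≥3 AEs, and whether each list is a minimum or exhaustive.
2. State in both places that AESIs of any grade are exempt from the restriction and are entered in the eCRF as well as reported under Section 13.3.3.
3. Specify in the SAP that the addendum shows AE rates separately before the cutoff, from the cutoff to Amendment 7, and after Amendment 7. Label the last period as related-only, noting the added events that changed treatment, and do not pool it into all-cause incidence.

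The cost is wording in two protocol sections, table footnotes in the addendum, and a few extra AE pages. Where data have already been collected under mixed rules, the third step can still be done without any new collection.
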